## 9.2.3 Serious Adverse Events

**Serious Adverse Event (SAE):** An SAE, as defined by the NIH, consists of adverse events that result in death, require either inpatient hospitalization or the prolongation of hospitalization, are life-threatening, result in a persistent or significant disability/incapacity or result in congenital anomaly/birth defect. Other important medical events, based upon appropriate medical judgment, may also be considered Serious Adverse Events if a trial participant’s health is at risk and intervention is required to prevent an outcome mentioned.

All SAEs will be recorded on the Serious Adverse Events Form (*Appendix D*), documented in the UE/SAE log and reported to the IRB. The SAE Form will be completed by the study coordinator, and includes information relating to the onset and nature of the SAE, relationship to the study treatment, seriousness of the SAE, treatment required as a response to the SAE, and outcome. This form will be filed in the

participant's binder at the resolution of the event. The study coordinator will complete the UE/SAE log (*Appendix E*) which includes information such as the date of the event, time at which the study team was informed of the event, details, when the IRB has been notified, and the date that the SAE Form was completed.

#### **9.2.4 Unanticipated Problems.**

Unexpected Events (UE) will be recorded on the UE/SAE log (*Appendix E*) and will include information such as the date of the event, when the study team was informed of this event, details of the event, when the IRB was notified, and whether the SAE Form was completed. The IRB will be notified of each UE that may occur during the study.

The Office for Human Research Protections considers unanticipated problems involving risks to participants or others to include, in general, any incident, experience, or outcome that meets all of the following criteria:

- Unexpected (in terms of nature, severity, or frequency) given (a) the research procedures that are described in the protocol-related documents, such as the IRB-approved research protocol and informed consent document; and (b) the characteristics of the participant population being studied;
- Related or possibly related to participation in the research
- Suggests that the research places participants or others at a greater risk of harm (including physical, psychological, economic, or social harm) than was previously known or recognized.

If an UE occurs the IRB will be notified and the study will be adjusted as needed to protect the health and safety of the participants. Depending on the nature of the UE, the research protocol, inclusion/exclusion criteria, and informed consent will be changed to reflect the possibility of this event reoccurring. *Please see Appendix F for an example of the Consent Amendment Tracking log.* During this time, no new participants will be recruited and the research procedures for currently enrolled participants will be stopped. Each UE will be recorded and reported throughout the study.

### **9.3 Reporting Procedures**

We will be adopting the follow table for reporting procedures:

What Event is Reported	When is Event Reported	By Whom is Event Reported	To Whom is Event Reported
Fatal or life-threatening unexpected, suspected serious adverse reactions	Within 24 hours of initial receipt of information	Investigator	
 
Local/internal IRBs, DSMB
 

Non-fatal, non-life-threatening unexpected, suspected serious adverse reactions	Within 48 hours of initial receipt of information	Study Coordinator	
 
Local/internal IRBs/Institutional Officials, DSMB
 

Unanticipated adverse device effects	Within 10 working days of investigator first learning of effect	Investigator	
 
Local/internal IRBs
 

Unanticipated Problem that is not an SAE	Within 7 days of the investigator becoming aware of the problem	Investigator	
 
Local/internal IRBs/Institutional Officials,
 

All Unanticipated Problems	Within 30 days of the IRB's receipt of the report of the UP from the investigator.	IRB	
 
OHRP
 

		Investigator 	
 
External IRBs
 

### 9.3.1 Reporting of Pregnancy

Pregnancy tests will be administered at the initial session to all women of child-bearing potential. There are no studies that suggest tACS would interfere with pregnancy. However, should a participant become pregnant during the study their participation will be immediately terminated and will be sent to consult with Co-I and medical monitor.

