## 4 STUDY DESIGN

The design for this pilot study is a randomized, double blind, sham-controlled, clinical trial which will be used to demonstrate feasibility and collect preliminary efficacy data for further refinement of a tACS approach. We are recruiting from a clinical population. For this clinical trial we are seeking 48 males and non-pregnant females ages 18-70 with diagnosis of schizophrenia or schizoaffective disorder, who have at least 3 auditory hallucinations per week, with no change in medication dosing for at least 4 weeks and have been clinically stable for at least 12 weeks, meaning no change in their level of care. All women of child-bearing potential will have a pregnancy test during the initial session in order to determine eligibility for the study. These individuals will be outpatients; most will be referred through psychiatrists in the UNC Department of Psychiatry and affiliated ACT clinics, or by mental health practitioners in the local community.

This is a single site, clinical trial with 3 arms. We estimate 2 years to complete study enrollment.

Participants will be randomly assigned to one of three arms; active sham stimulation, 10 Hz (alpha) tACS or 2 mA tDCS. Active sham treatment will include 10 seconds of ramp in to 1 minute of 10 Hz tACS with a ramp out of 10 seconds for a total of 80 seconds of total stimulation. The choice of an active sham is motivated to enhance success of patient blinding by mimicking skin sensations associated with tACS. 10 Hz and 2 mA tDCS will have a 10 second ramp in and ramp out with 20 minutes of stimulation for a total of 1180 seconds twice daily for one week. Stimulation waveform is a sine-wave with a peak-to-peak amplitude of 2 mA. In each arm, participants will stay in a relaxed and yet controlled state by watching a nature movie such as “Reefscape” during stimulation.

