### **5.2 Participant Exclusion Criteria**

A potential participant who meets any of the following criteria will be excluded from participation in this study:

- DSM-IV diagnosis of alcohol or substance abuse (other than nicotine) within the last month or a DSM-IV diagnosis of alcohol or substance dependence (other than nicotine) within the last 6 months
- Medical or neurological illness (unstable cardiac disease, AIDS, malignancy, liver or renal impairment) or treatment for a medical disorder that could interfere with study participation
- History of traumatic brain injury that required subsequent cognitive rehabilitation, or caused cognitive sequelae
- A difference of greater than 20% in AHRS scores between Consent Visit and Screening Visit.
- Prior brain surgery
- Any brain devices/implants, including cochlear implants and aneurysm clips

- Co-morbid neurological condition (e.g. seizure disorder, brain tumor)
- Non English speakers
- Female participants who are pregnant, nursing, or unwilling to use an adequate method of contraception during study participation for those of childbearing potential.
- Anything that, in the opinion of the investigator, would place the participant at increased risk or preclude the participant's likelihood of completing all components of the study

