## 6.2 Preparation and Administration of Study Investigational Product

After participants have completed the daily questionnaires, they will be comfortably seated. The research team will first measure their heads electrode placement using the 10-20 system. Participants will then be fitted with the 3 electrodes for stimulation. The participant will be in the

relaxed yet, experimentally controlled state by watching a nature movie. One session of stimulation will be performed twice daily, for 20 minutes. In the 10 Hz tACS and 2mA tDCS groups stimulation will have a 10 second ramp in and ramp out with 20 minutes of stimulation for a total of 1220 seconds. Stimulation waveforms are sine-waves with a peak-to-peak amplitude of 2 mA. The sham stimulation will include 10 seconds of ramp in to 1 minute of 10 Hz tACS with a ramp out of 10 seconds for a total of 100 seconds of stimulation. We will be using 5x5cm electrodes covered in 10/20 conductive paste and placed between Fp1 and F3 and between T3 and P3 with a 5x7cm electrode placed over CZ as a return electrode.

Stimulation devices will be preprogrammed and codes will be randomized to one of the three experimental arms. Researchers will enter the participant-specific code into the App that controls the stimulation and monitor participants during the 20 minutes of the stimulation.

The study coordinator and/or the research assistant will be thoroughly trained and have trainings documented on the transcranial stimulation device and will be present during all stimulation sessions. *Please see Appendix S for an example of the training documentation log.* To monitor side effects of stimulation a daily questionnaire will be administered after each stimulation session. *Please see Attachment 1 for an example of the daily stimulation questionnaire, and Attachment 2 for an example of the endpoint stimulation questionnaire.*

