## 7.2 Enrollment/Baseline

### Initial Screening Visit (Visit 1, Day 0)

At the consent visit, participants will sign both a HIPAA authorization form and the consent form. Each form will be read to the participant by the researcher, and the participant will be given the time to ask any questions about the information discussed. The researcher will verify that the participant meets inclusion criteria. If the participant is female, she will be asked to provide urine for a pregnancy test. All participants (male and female) will be asked to complete a urine drug screening to determine eligibility for the study. Next, the SCID (*Attachment 6*) will be administered in order to confirm diagnosis of schizophrenia or schizoaffective disorder and to verify that the participant does not have active alcohol or illicit drug abuse or dependency. Once the diagnosis has been confirmed, demographic information will be collected, which will include a history of medication, alcohol, and drug use and information about symptom onset and baseline vitals will be taken. A short handedness questionnaire and a Belief about Treatments questionnaire will also be administered. Each participant will be asked a series of questions (*Appendix H*) to ensure that the consent form is fully understood. After consent has been obtained, a baseline Auditory Hallucinations Rating Scale (AHRS) will be administered to document hallucinatory severity and frequency. The 2nd screening visit will be scheduled for approximately 2 weeks later, and the participant will be paid.

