## **8.2 Laboratory Evaluations**

### **8.2.1 Clinical Laboratory Evaluations**

During the initial session, all participants will be asked to participate in a urine drug screen in order to help screen out any individuals who have a drug use problem. A urine pregnancy test will also be performed for any female participant who is unable to confirm pregnancy status. This information will be recorded on the inclusion/exclusion criteria checklist (*Appendix M*) to be completed by the researcher. Participants will also be asked to complete a drug urine test during the initial session to verify drug use status.

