### **13.4 Exclusion of Women, Minorities, and Children (Special Populations)**

Non-English speaking individuals are excluded because the ability to accurately and completely communicate study information, answer questions about the study, and obtain consent is necessary. Female participants will be asked if there is any reason to believe they might be pregnant. Pregnant participants will be excluded despite the fact that theoretical risk to mother or fetus is exceedingly small, since no safety data for pregnancy is known to exist for transcranial

current stimulation studies. All women of child-bearing potential will be asked to take a pregnancy test during the initial session in order to determine eligibility for the study.

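### The only pregnancy test falls about 2 to 6 weeks, plus an unstated scheduling lag, before first stimulation; a repeat on Day 1 would be a cheap safety gain

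*Combined protocol and SAP*

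**What the plan says.** On timing, the text is consistent. Section 9.3.1: "Pregnancy tests will be administered at the initial session to all women of child-bearing potential". Section 4: "All women of child-bearing potential will have a pregnancy test during the initial session in order to determine eligibility for the study". Section 7.2, under the initial screening visit (Day 0): "If the participant is female, she will be asked to provide urine for a pregnancy test". Section 13.4 also names the initial session, and the schematic lists beta-HCG, at 5 minutes, under the initial screening session only. For Day 1, section 7.3 lists vital signs, AHRS, PANSS, BACS and CGI-S, followed by stimulation. The Day 1 cell of the schematic agrees, and neither includes a pregnancy test. No later visit has one either.

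On who is tested, the text differs. Sections 4, 9.3.1 and 13.4 refer to all women of child-bearing potential, and section 7.2 to any female participant. Section 8.2.1 is narrower: "A urine pregnancy test will also be performed for any female participant who is unable to confirm pregnancy status".

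On the reason for the exclusion, section 13.4 explains that pregnant women are kept out although the "theoretical risk to mother or fetus is exceedingly small, since no safety data for pregnancy is known to exist for transcranial" current stimulation studies. The clause about missing data is the reason for excluding them, not for calling the risk small. Section 9.3.1 adds: "There are no studies that suggest tACS would interfere with pregnancy". It then ends participation at once if a pregnancy occurs.

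**The concern.** The exclusion rests on unknown effects of stimulation in pregnancy, so the moment at which status matters most is when current is first applied. The plan checks status objectively only once, at the start of a screening period of variable length, and not again before exposure. A team that followed the protocol exactly could stimulate a woman whose pregnancy began, or remained unrecognised, after the initial session. Section 8.2.1 adds a second weakness. Read on its own, it would let a woman of child-bearing potential who says she is not pregnant go untested even at the initial session. What is at stake is participant safety and the integrity of one eligibility criterion, not the efficacy comparison.

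**Working it through.** The check is calendar arithmetic and a comparison of sections.

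**Inputs**
- Test at the initial visit, week 0 (sections 4, 7.2, 9.3.1, 13.4; schematic).
- Screening visits about 2 weeks apart (sections 4 and 7.2).
- Up to two further screening visits after the 2nd if the AHRS is not stable, within a maximum of 6 weeks (section 4).
- Lag L from the qualifying visit to Day 1: not stated. Section 7.2 says only that the stimulation week is scheduled once eligibility is confirmed.

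**Reproducing the plan's own figure.** Visit k falls at week 2 × (k − 1). Visits 1, 2, 3 and 4 therefore fall at weeks 0, 2, 4 and 6. The longest screening period is 3 × 2 = 6 weeks, which matches section 4.

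**Age of the test at first stimulation.** Gap = week of the qualifying visit − 0 + L:
- stable at the 2nd visit: 2 weeks + L
- stable at the 3rd visit: 4 weeks + L
- stable at the 4th visit: 6 weeks + L

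Because L is not given, the values below are assumptions that only show how the range moves:
- L = 1 week: 3 to 7 weeks
- L = 2 weeks: 4 to 8 weeks
- L = 4 weeks: 6 to 10 weeks

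With a repeat test on Day 1 before the first session, the gap is 0 days whatever L is.

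**What covers the interval**
- Section 5.2 excludes women of child-bearing potential who are "unwilling to use an adequate method of contraception during study participation". This is an undertaking, not a check.
- Section 7.1 asks about pregnancy by telephone, before the initial visit. Section 13.4 has a similar question. Both are self-report.
- Section 5.4.2 withdraws a participant who newly meets an exclusion criterion, and section 9.3.1 ends participation on pregnancy. Both act only once someone knows.

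None of these objectively verifies status between the initial session and the first current.

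**Number affected.** The documents give no count of women of child-bearing potential, no pregnancy rate and no lag. An expected number cannot be derived from them, so none is offered. With 48 participants in total and contraception required, it is probably below one.

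**The case against.** The strongest reply is that a single test is a legitimate design choice. Sections 4 and 13.4 give its purpose as determining eligibility, and a screening test serves that purpose. The interval is covered by required contraception, direct questions, and withdrawal or termination. The sponsor regards the theoretical risk as exceedingly small and knows of no study suggesting interference. A Day 1 test would also be only a partial remedy: of the 10 planned sessions, the remaining 9 and all follow-up would still rest on the same controls.

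Much of this stands, and it keeps the severity low. No rule in the protocol is broken. That the exclusion should be re-verified at first exposure is an inference from the stated reason for it, not something the documents say. What does not stand is the idea that the other controls do the work of a test, since they depend on an undertaking, on self-report, or on a pregnancy already being known.

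Two stronger readings are tempting and not supported. A reader might infer that pregnant women are likely to be exposed or harmed. The documents supply no rates and describe the risk as very small. A reader might also infer from Appendix A that the schedule contradicts the text about which visit holds the test. The column headings are not legible in the text available, so nothing can be built on that. The single beta-HCG mark there sits in a column before randomization and first stimulation, so it does not supply a Day 1 test.

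**Conclusion.** The point holds as a modest safety improvement. On the text and schematic, the only pregnancy test is about 2 to 6 weeks old, plus an uncapped scheduling lag, at first stimulation, and no Day 1 test is listed. The range is approximate because visits are only approximately 2 weeks apart. It also assumes that the footnote marked on beta-HCG in the schematic, whose text is not shown, does not add a later test. The conflict between section 8.2.1 and sections 4, 9.3.1 and 13.4 is real whether or not a repeat is added. Severity is low: few if any women are likely to be affected, and the AHRS comparison, the analysis and the sample size do not change.

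**What to change.** Keep the initial test, which serves as an early eligibility check. Repeat the urine test for all women of child-bearing potential on Day 1, with the result known before the step in section 6.2 where "Researchers will enter the participant-specific code into the App that controls the stimulation". Add the repeat to the Day 1 procedures in section 7.3 and the schematic, and to the testing statement in section 9.3.1. Reword section 8.2.1 so that it covers all women of child-bearing potential, as sections 4, 9.3.1 and 13.4 do.

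The cost is one urine strip per woman of child-bearing potential, about 5 minutes on the schematic's own timing, at a visit that already takes place, plus the wording changes. The repeat verifies status at first exposure only. A pregnancy arising later would still be handled under sections 5.4.2 and 9.3.1.

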## 9.4 Type and Duration of Follow-up of Participants after Adverse Events

Medical monitors and Co-I will follow up with participants within one week of an AE.

## 9.5 Halting Rules

If a seizure occurs at the time of a study visit, a temporary hold will be placed over the study and further investigation will ensue. This could lead to stopping the study prematurely or continuing on with further safety measures in place. If two seizures are witnessed during the study visits, the entire study will be stopped prematurely. These individuals would be referred for further medical attention. It is very unlikely that a seizure will occur, given that previous studies using tDCS in

patients with depression and schizophrenia have had no seizures occur (Berlin et al., 2013, Brunelin et al., 2012). The study will also be stopped if other studies provide evidence that transcranial current stimulation has been associated with other, previously unrecognized, potentially harmful effects, either short-term or long-term.

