*Risk of Injury and Discomfort:* Transcranial current stimulation has been used without any reports of serious side-effects for more than a decade. This stimulation mode has NOTHING to do with electroconvulsive therapy that applies many orders of magnitude higher stimulation current. Rather, transcranial current stimulation is so weak that it does not cause super-threshold activation of neurons ([name] and McCormick, 2010). In particular, tACS has been used without reports of any serious side-effects. Some participants report a transient mild tingling, burning, or itching underneath the electrodes and headache, but no other side effects have been noted. Importantly, it remains unclear

if these mild side-effects were caused by the transcranial brain stimulation. In order to monitor these side-effects, we will be administering an adverse effects stimulation questionnaire (*Attachments 1 &2*) after each stimulation session to determine whether these effects were experienced. Research personnel present during these sessions will also check in with the participant periodically during the stimulation to see whether they are comfortable. If any side-effect occurs (rated by the participant as stronger than “moderate”) or the participant is experiencing severe discomfort, the stimulation will be immediately stopped.

While not previously reported with tDCS or tACS in humans, there is a theoretical possibility that stimulation of neuronal circuits could lead to epileptic discharges. To minimize this occurrence, we screen and exclude patients with personal and family history of neurological conditions from the study. If abnormalities or a seizure is witnessed during the course of the study, the subject will be referred to a neurology clinic for further evaluation and treatment.

We have no evidence that our treatment paradigms will increase auditory hallucinations if not treated (receive the sham treatment), as participants, will be by definition, stable. If an enrolled patient shows signs of increase symptoms that were not apparent during enrollment, a referral to UNC Psychiatry will be made. [name], Co-I, will facilitate this process.

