## **9.6 Safety Oversight**

Safety oversight will be under the direction of a DSMB composed of [name], an epidemiologist, a biostatistician and one or more clinical researchers. The DSMB will review AEs every 6 months whereas the medical monitor will review AEs in real time and make decisions as to each participant's continuation in the trial. The PI will review AEs weekly with research team and may request additional review by Co-I on a case-by-case basis. The medical monitor will also be present at weekly meetings in order to discuss/explain any event(s) that may occur.

Every 6 months DSMB will review blinded AE reports. If there is reason to view unblinded information, the DSMB will directly receive the list of participants' identification numbers from a [name] Lab member, not otherwise associated with this clinical trial. Participant identification number will be displayed in a table according to the three arms of the study; however the specific treatment of that arm will not be disclosed. This will allow the DSMB to compare the three treatment groups.

Reasons for stopping the study and asking for further investigation include; decrease in cognitive abilities based on baseline and end of study data (>25% decrease in scores in 2/10 of the first participants or 20% of participants overall.). In addition, as mentioned above, if a seizure occurs during a study visit, the clinical trial will be temporarily be placed on hold for further investigation.

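### The automatic one-seizure hold covers only seizures at a study visit, so a documented seizure at home triggers no set study-wide pause; separately, no DSMB notice time is set for any seizure

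*Combined protocol and SAP*

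**What the plan says.** Section 9.5 (Halting Rules) has two seizure rules. The first is the hold: "If a seizure occurs at the time of a study visit, a temporary hold will be placed over the study". The second is the stop: "If two seizures are witnessed during the study visits, the entire study will be stopped prematurely". Section 9.6 (Safety Oversight) restates the first with the same limit: "if a seizure occurs during a study visit, the clinical trial will be temporarily be placed on hold".

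Section 2.3.1 looks more widely in time, but acts only on the individual: "If abnormalities or a seizure is witnessed during the course of the study, the subject will be referred to a neurology clinic".

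On oversight, 9.6 says "The DSMB will review AEs every 6 months", and that "the medical monitor will review AEs in real time and make decisions". Those decisions concern whether each participant stays in the trial.

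A study-wide pause that does not depend on location appears in 9.2.4. While the study is being adjusted after an unexpected event, "no new participants will be recruited and the research procedures for currently enrolled participants will be stopped". The criteria listed there must all be met, and they begin: "Unexpected (in terms of nature, severity, or frequency) given (a) the research procedures". The other two are that the event is at least possibly related to the research, and that it suggests more risk than was known before.

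Section 9.3 sends unexpected, suspected serious adverse reactions to the IRB and the DSMB: within 24 hours if fatal or life-threatening, otherwise within 48 hours.

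**The concern.** The sponsor chose a single seizure as enough reason to hold the study. A documented seizure in the evening after a stimulation is informative about the participants still being stimulated, just as one in the clinic is. As written, only the second produces a hold by rule. For the first, whether others go on being stimulated rests on how the event is classed and on judgement.

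The DSMB question is a separate gap. A seizure that is not classed as an unexpected, suspected serious reaction carries no timed notice to the DSMB, wherever it happens. The next scheduled DSMB look could then be up to 6 months away.

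**Working it through.** **Routes from an off-visit seizure to a study-wide hold**

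| Section | What it does | Automatic study-wide hold? |
|---|---|---|
| 9.5, 9.6 | Hold after one seizure, stop after two | No: visits only |
| 2.3.1 | Neurology referral | No: participant only |
| 5.4.2 | Withdrawal if an exclusion criterion newly develops | No: participant only |
| 9.4, 14.4 | Follow-up within one week; medical monitor told within 24 h, PI within 72 h | No |
| 9.6 | Real-time monitor review, weekly PI review | No: judgement |
| 9.2.3 | SAEs reported to the IRB | No |
| 9.2.4 | Recruitment and procedures stop | Only if unexpected, at least possibly related and suggesting greater risk |
| 5.4.4 | Investigator may end the study | No: discretion |

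**Routes to prompt DSMB notice.** Only the first two rows of the 9.3 table name the DSMB, and they need the event to be unexpected, suspected and serious. The rows for unanticipated device effects (10 working days) and for non-SAE unanticipated problems (7 days) do not list the DSMB. Section 9.2.3 names the IRB but not the DSMB. Sections 9.5 and 9.6 give no DSMB time for a seizure at a visit either.

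**How firm the classification is.** Section 9.2.2, headed Expected Adverse Reactions, mentions seizure as a theoretical possibility. Section 9.2.1 calls an event associated only if it is temporally related and nothing else explains it. Both leave room for dispute over an unobserved event at home.

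**Time outside the rule**

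Inputs are the visit lengths in Section 4: 6 h on Day 1, 4.5 h on each of Days 2 to 4, 9 h on Day 5.

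- Check on the inputs, all visits: 2 + 3 + 6 + 3 × 4.5 + 9 + 2.5 + 5 = 41 h. Two extra screening visits add 6 h, giving 47 h. This reproduces the protocol's 41 to 47 hours.
- Visit time in the stimulation week: 6 + 3 × 4.5 + 9 = 28.5 h.
- Start of Day 1 to end of Day 5, assuming equal start times: 4 × 24 + 9 = 105 h.
- Outside visits: 105 − 28.5 = 76.5 h; 76.5 / 105 = 73%.
- The visit lengths include the 3-hour break. For Days 2 to 4 the schematic gives 5 + 40 + 1 + 180 + 40 + 1 = 267 min = 4.45 h. If the break is not treated as being at a visit, the off-visit time is 76.5 + 5 × 3 = 91.5 h, or 87%.

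**Stimulations followed by a night away.** On Days 1 to 4 the second stimulation is followed only by a short questionnaire and payment. That is 4 of 10 stimulations per participant: 4 × 48 = 192 of 480 overall, and 4 × 32 = 128 of 320 in the two active arms.

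**Exposure before the next scheduled DSMB review.** Assuming even enrolment, 48 / 24 = 2 per month. At most 6 × 2 = 12 participants, of whom 12 × 2/3 = 8 in active arms, would start in a 6-month gap. This upper limit assumes that nobody else pauses the study first.

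**Participants whom a hold would affect.** 48 / 104 weeks = 0.46, so about 0.5 participants are in their stimulation week at any time.

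**The case against.** The strongest case is that a pause independent of location already exists in 9.2.4, and that a seizure would probably qualify. Section 2.3.1 says none has been reported with these methods in humans, 9.5 calls one very unlikely, and seizure disorder is an exclusion. The reactions that 9.2.2 reports as actually seen are tingling, burning, itching and headache; seizure is a separate theoretical remark. A rule tied to visits also catches observed events close to stimulation, with the rest left to a medical monitor told within 24 hours. The stopping reasons in 9.6 are not presented as a complete list.

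Much of this stands. A reader might infer that an at-home seizure could never pause the study or reach the DSMB quickly. The documents do not support that: 9.2.4 and 9.3 can do both. They do not guarantee either, since each depends on several judgements.

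A reader might also infer that the visit limit causes the missing DSMB notice. It does not. Sections 9.5 and 9.6 set no notice time for a seizure at a visit, and the 9.3 table takes no account of location.

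Nor do the 73% and 87% measure harm. They count clock hours, and the documents give no seizure rate and no timing of seizures relative to stimulation.

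**Conclusion.** The point holds as two separate gaps. First, the automatic hold is confined to visits, so a documented off-visit seizure produces no study-wide hold by rule; whether there is a pause depends on all three 9.2.4 criteria or on discretion. Second, no DSMB notice time is set for any seizure as such.

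By the clock, 73% of the stimulation course lies outside visits, or 87% if breaks are not visit time. This rests on the Section 4 visit lengths and equal start times.

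Care of the affected participant is adequate as written; what is missing is a study-level rule. This is worth changing because the change is small, not because a seizure is likely.

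**What to change.** In 9.5 and 9.6, in matching words:

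- Apply the temporary hold to any seizure witnessed or medically documented from first stimulation to the one-month visit, wherever it occurs, including the 3-hour break.
- Notify the DSMB of any seizure, on or off visit, within the times already in 9.3: 24 h if fatal or life-threatening, otherwise 48 h.
- Keep the automatic two-seizure stop for seizures witnessed at visits. After an off-visit seizure, let the DSMB decide whether the study continues, taking relatedness into account.

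Do not add a blanket statement that every seizure is unexpected for 9.2.4. If that alone triggered the 9.2.4 pause, it would duplicate the hold with a longer stop while the protocol and consent are revised. If all three criteria are required, it would not trigger the pause by itself.

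The cost is wording in two sections, with no new visit or procedure. The downside is that an unrelated off-visit seizure, even in the sham arm, would cause a temporary hold and an extra DSMB review. A hold of one full day means two consecutive missed stimulations, which could end participation under 5.3 for anyone in the stimulation week: about 0.5 participants at even enrolment. The existing hold has the same effect.
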